## **3.0 PATIENT SELECTION CRITERIA**

### **3.1 Eligibility Criteria**

- Diagnosis of invasive ductal, medullary, papillary, colloid (*mucinous*), tubular histologies or Ductal carcinoma in situ (DCIS)
- Tumor stage: Tis, T1, T2 if lesion  $\leq 3$  cm
- Nodal Stage: N0 (*or a negative sentinel node mapping is acceptable*) or N1 (*1-3 nodes positive and no extracapsular extension*). This represents a cohort of patients that would not ordinarily receive axillary irradiation. (subjects with DCIS are exempt from nodal staging)
- Clearly visible target as defined by ultrasound, surgical clips, or mammography
- Unifocal breast cancer (*single focus which can be encompassed by one lumpectomy*)
- Negative microscopically-assessed surgical margins
- Negative post-lumpectomy mammogram if cancer presented with malignancy-associated microcalcifications
- No Paget's disease of the nipple or EIC by the Harvard definition, i.e. 1) more than 25% of the tumor is DCIS and there is DCIS in adjacent breast tissue, or 2) an intraductal carcinoma with microinvasion.
- No collagen vascular disease (systemic lupus erythematosis, scleroderma, or dermatomyositis)

- No previous radiation or chemotherapy for current breast cancer
- No co-existing medical conditions with life expectancy < 2 years
- Age > 18 years old
- No pregnant or lactating women.
- No psychiatric or addictive disorders which would preclude obtaining informed consent or completing the full series of brachytherapy treatments on an outpatient basis.
- Signed study-specific consent form

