## **10.0 STATISTICAL CONSIDERATIONS**

### **10.1 Study Endpoints**

#### **10.1.1 Ipsilateral breast recurrences**

This is a one-arm equivalence trial comparing the local failure rate in 300 patients receiving brachytherapy to the historical mean event rate of 6% (see Table below) among patients given external beam radiation. The null hypothesis thus is that brachytherapy is worse than external beam radiation; the alternative hypothesis is that the two regimens are clinically equivalent, meaning that brachytherapy is not significantly worse than external beam. Symbolically

$$H_0: \text{Pr}(\text{Local Failure, brachy.}) > \text{Pr}(\text{Local Failure, EB}) + \Delta$$

$$H_A: \text{Pr}(\text{Local Failure, brachy.}) \leq \text{Pr}(\text{Local Failure, EB}) + \Delta,$$

where "Pr()" denotes the probability of its argument and  $\Delta$  is the margin of clinical equivalence. That is, we consider two regimens whose event probabilities differ by less than  $\Delta$  to be equivalent. For this study we take  $\Delta$  to be 5%.

The analysis will be conducted by calculating an exact 95% confidence interval for the probability of local failure in the brachytherapy group and noting whether it includes 11% (obtained as  $\text{Pr}(\text{Local Failure, EB}) + \Delta = 6\% + 5\%$ ). If it does then we will not reject the null hypothesis and equivalence cannot be concluded. If the confidence interval for the probability of local failure given brachytherapy falls entirely below 11% then we conclude that brachytherapy is clinically equivalent (or possibly superior) to external beam radiation as a treatment for these patients. If, among 300 patients, there are 23 local failures (7.7%) then the exact 95% confidence interval for the true failure rate will be (5.2%, 11.2%). If there are 22 failures (7.3%) then the confidence interval will be (5.0%, 10.8%). Therefore we will reject the null hypothesis and conclude equivalence if we observe 22 or fewer local failures.

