Power here is the probability that we will reject the null hypothesis and conclude equivalence given that it truly holds. If the two regimens rates are identical, such that  $\text{Pr}(\text{Local Failure, brachy.}) = \text{Pr}(\text{Local Failure, EB}) = 6\%$ , then the power with 300 patients is 86%. If the brachytherapy rate is inferior to external beam by 2%, so that  $\text{Pr}(\text{Local Failure, brachy.}) = 8\%$  and  $\text{Pr}(\text{Local Failure, EB}) = 6\%$  (which is still within our definition of clinical equivalence) then power drops to 39%. However if the brachytherapy rate is superior to external beam by 2% so that  $\text{Pr}(\text{Local Failure, brachy.}) = 4\%$  and  $\text{Pr}(\text{Local Failure, EB}) = 6\%$  then the power is 99.8%. Therefore if the local failure is 6% or less in the brachytherapy group then this study is well-powered to conclude equivalence within a margin of 5%.

Study	# Patients	5-year LF Rate (%)	Weighted LF rate
French	88	4.5	396
NSABP B-06	628	5	3140
NCI	121	2	242
Danish	430	5	2150
EORTC	456	11	5016
Milan	352	3	1056
Total/Mean	2075	5.08	5.78%

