### **10.2 Study Design**

The sample size will be approximately 300 patients. The toxicity rate will be summarized along with exact 95% confidence intervals. DFS, MFS and OS

results will be summarized using Kaplan-Meier curves with the usual Greenwood estimates of standard errors. Summary statistics will be given for cosmesis, quality of life, dosimetric, and mammography interpretation measures. All analyses will be conducted on an intent-to-treat basis; that is, all registered patients will be included in the analyses.

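### The 86% power is right for 300 patients with known 5-year status, but it needs essentially complete follow-up, and the plan makes no allowance for loss

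*Combined protocol and SAP*

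**What the plan says.** Section 10.1.1 compares brachytherapy with a "historical mean event rate of 6" per cent for external beam and adds a margin of 5 points. The analysis consists of "calculating an exact 95% confidence interval for the probability of local failure in the brachytherapy group" and "noting whether it includes 11" per cent. For 300 patients this becomes a fixed count: the plan will "conclude equivalence if we observe 22 or fewer local failures".

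For a true rate of 6% the same section states: "then the power with 300 patients is 86" per cent. At a true 8%, "then power drops to 39" per cent; at 4% it is given as 99.8%. The section concludes that the study is well powered if the true rate is 6% or less.

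The endpoint has a 5-year horizon (Sections 2.1 and 8.2). Section 10.2 says "The sample size will be approximately 300 patients", keeps all registered patients in every analysis, and plans Kaplan-Meier curves for disease-free, mastectomy-free and overall survival, but not for local failure. Section 3.1 requires "No co-existing medical conditions with life expectancy < 2 years", so patients who may die before 5 years can enter. Section 8.1 (note c) and Section 9.1 let follow-up come from other physicians' notes or by telephone.

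**The concern.** The printed powers treat each of 300 patients as a yes-or-no result known at 5 years. The plan neither secures that nor says what happens otherwise. With about 300 registered and nothing added, any patient whose 5-year status is unknown must be left out, censored, or assigned a result. The first two reduce the information behind the confidence limit. Assigning a result of no failure protects the power but makes the 95% limit too optimistic.

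At stake is what a reader makes of the result. If equivalence is not shown, the chance that this happened to a treatment with a true 6% rate matters, and it may be larger than the 14% implied by the plan (100% - 86%). If equivalence is shown with missing patients counted as successes, the error rate behind that conclusion is above the nominal 2.5%.

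**Working it through.** **Inputs from the plan.** n = 300; limit 6% + 5% = 11%; exact two-sided 95% interval; cut-off 22; true rates 6%, 8% and 4%. **Assumed:** 5%, 10% and 20% of patients not observed to 5 years.

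**1. Reproducing the plan.** The cut-off is the largest x whose Clopper-Pearson upper 95% limit is below 11%. At n = 300 the upper limit is 10.9% for 22 failures and 11.3% for 23, so the cut-off is 22. (The printed intervals differ slightly from these exact ones; the cut-off does not change.) Power = P(X ≤ 22 | 300, p):
- p = 6%: 86.2% (printed 86%)
- p = 8%: 38.5% (printed 39%)
- p = 4%: 99.75% (printed 99.8%)
- error at p = 11%: 2.2%

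**2. Evaluable patients only, cut-off recomputed.** n = 300 × (1 - loss); power = P(X ≤ cut-off | n, p).

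| Evaluable | Loss | Cut-off | Power at 6% | at 8% | at 4% |
|---|---|---|---|---|---|
| 300 | 0% | 22 | 86.2% | 38.5% | 99.8% |
| 285 | 5% | 20 | 80.5% | 31.6% | 99.4% |
| 270 | 10% | 19 | 80.4% | 32.8% | 99.3% |
| 240 | 20% | 16 | 72.5% | 26.7% | 98.3% |

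Because the cut-off is a whole number, power moves in a sawtooth. At 6% it is 86.9% for n = 298, 81.8% for 297, 85.6% for 287, 78.2% for 275 and 84.2% for 276. Between 270 and 285 it ranges from 78.2% to 84.2%. Below 300, only 298 and 299 reach 86%; no n from 240 to 297 does. The tolerance is thus 2 patients in 300, or 0.7%.

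**3. Kaplan-Meier at 5 years, all 300 included.** Simulated with exponential failure (6% by year 5), exponential loss, and an upper 95% limit (log-log scale) compared with 11%. Simulations of 4,000 to 20,000 runs give power of about 86% with no loss, 83% at 5%, 82-83% at 10% and 78-80% at 20%. Error at a true 11% stays at about 1.8-2.3%. With 10% loss, a 20,000-run simulation gives 82% at a true 6%, 34% at 8% and 99% at 4%.

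**4. The 22-of-300 rule on all registered patients, lost patients counted as failure-free.** With λ = -ln(1 - p) and μ = -ln(1 - d) on the 5-year scale, where d is the loss, the chance that a failure is observed is q = λ/(λ + μ) × [1 - (1 - p)(1 - d)].

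Example, p = 11% and d = 10%: λ = 0.1165, μ = 0.1054, q = (0.1165/0.2219) × 0.199 = 0.1045, and P(X ≤ 22 | 300, 0.1045) = 4.2%.

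| Loss | q at 6% | Power | q at 11% | Error at 11% |
|---|---|---|---|---|
| 5% | 0.0585 | 88.6% | 0.1073 | 3.1% |
| 10% | 0.0570 | 90.7% | 0.1045 | 4.2% |
| 20% | 0.0538 | 94.2% | 0.0988 | 7.9% |

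**5. Lost patients counted as failures.** At 5% loss the effective rate is 0.06 + 0.05 × 0.94 = 0.107, and power under the 22-of-300 rule is 3%. At 2% loss it is 41%.

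**The case against.** There is no arithmetic error: the plan says the power is for 300 patients, and all three figures reproduce. A reader might nevertheless infer that the design in fact delivers only about 80% power. The documents do not support that. They give no loss rate, and the lower figures belong to analyses the plan does not specify. An evaluable-only analysis conflicts with Section 10.2, and Kaplan-Meier is planned there only for other endpoints. Under the written rule, with lost patients taken as failure-free, power goes up. Nor is it true that 86% needs every one of the 300: 298 or 299 give slightly more, and several smaller numbers come within 2 points.

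Loss may also be small. Follow-up by telephone or through other physicians limits it. The definition in Section 8.2 allows a patient who dies without recurrence to be read as a known non-failure rather than as unobserved, and the life-expectancy criterion gives no death rate. At the plan's own weighted historical rate of 5.78%, power is 89.6% with 300 patients and still 84.5% with 270.

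All of this stands, and it limits the size of the point. It does not remove it. Including every registered patient does not supply a missing 5-year result, and the reading under which power survives is the one that inflates the error rate.

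**Conclusion.** The point holds as a modest one. The printed powers are correct but conditional on essentially complete 5-year follow-up, a condition the plan neither states nor provides for. Once more than about 1% of patients lack 5-year status, none of the ways of handling them examined here gives both 86% power and the stated 95% confidence level. With the limit kept valid, the likely cost at 5-10% loss is a few points, to roughly 80-83% at a true 6%. At 20% loss, power is 72.5% (evaluable only) or about 79% (Kaplan-Meier). With the count rule kept and lost patients taken as failure-free, the cost appears as error instead: 3.1%, 4.2% and 7.9% at 5%, 10% and 20% loss, against 2.2%.

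These sizes rest on assumed loss rates, on loss unrelated to recurrence and, in steps 3 and 4, on exponential failure and loss. They do not show that the trial is too small, and they do not overturn the conclusion that power is reasonable at 6% or less.

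**What to change.** In Section 10.1.1:

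- Label 86%, 39% and 99.8% as figures for complete 5-year follow-up.
- Replace the fixed 22-of-300 count with a 5-year failure probability estimated by a method that handles censoring, with all registered patients included, and compare its upper 95% limit with 11%. Kaplan-Meier and cumulative incidence are both suitable. State in advance which is used, how death without recurrence is treated, and how the limit is computed.
- Write down the assumed proportion not observed to 5 years and restate power for it. For example, with 300 registered and 10% lost under Kaplan-Meier: about 82-83% at a true 6%, 34% at 8% and 99% at 4%.

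This takes a few sentences and no added enrolment. If follow-up proves complete, the new analysis has about the same power as the old rule (about 86%). The cost is a slightly lower stated power and the loss of a simple pass count.

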### **10.1.2 Toxicity Assessment**

Patient will be seen on a daily basis by treating physician while receiving radiation therapy and during each follow-up visit. Toxicities resulting from brachytherapy will be collected and graded according to the Modified RTOG Toxicity Criteria (appendix). Any toxicities grade 3 or higher will be promptly reported to DSMB and IRB.

### **10.1.3 Cosmesis**

Cosmetic results will be assessed by both the physician and the patient pre-brachytherapy, at six and twelve months, then annually. Photographs are to be taken at these time points according to the specifications in Section 8.5.

### **10.1.4 Quality of Life Assessment**

Patient satisfaction with breast brachytherapy will be assessed by a questionnaire at defined intervals: pre-brachytherapy, at completion, 4-6 weeks post-brachytherapy, 6 months post-brachytherapy and annually thereafter. (attached forms)

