## **2.2 Secondary Objectives**

- To determine if brachytherapy will have non-inferior toxicity to external beam radiotherapy (5%) at 3 years. Grade 3 or higher toxicity will be scored.
- To evaluate cosmesis at each follow-up by utilizing a cosmesis score based on established Harvard criteria.
- To assess patient satisfaction with breast brachytherapy by a questionnaire pre-brachytherapy, at completion, and post-brachytherapy.
- To perform a dosimetric comparison with an external beam plan for each patient. The following parameters will be evaluated: skin dose, target coverage, dose homogeneity index, and NTDmeans from dose volume histograms for each individual patient for heart, lung, and contralateral breast.
- To assess the ability to interpret mammography after interstitial brachytherapy.
- To evaluate Disease-free, Mastectomy-free, and Overall Survival.

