## **8.0 PATIENT ASSESSMENTS**

### **8.1 Study Parameters**

Assessment	Pre Rx	During/After Brachytherapy	Post RX 4-6 weeks	Post RX 6 mos.	Post RX 1 year
H & P (Initial Eval Form)	X				
Chest x-ray	X				
Lab studies a	X				
H & P (Follow-up Form)			X	X	Xc
Disease status	X		X	X	Xc
Toxicity Assessment		X	X	X	Xc
Mammograms	Xd			X	Xe
Cosmesis, Pt (Form)	X			X	Xb
Cosmesis, MD (Form)	X			X	Xb
Photographs	X	X	X	X	Xc
Questionnaire (QOL)	X	X	X	X	Xb

- a. CBC, platelets, PTT, PT, BUN, creatinine, lytes
- b. Yearly thereafter upto 5 years.
- c. Clinical examination and disease status assessment at 6 month intervals for the first 5 years and yearly intervals thereafter. (Can be done via clinic visit notes from other physicians involved in patient's care or via telephone follow-up).
- d. pre and post lumpectomy (if applicable)
- e. Every 6 months for 3 years and then yearly for 5 years (for treated breast) and yearly for opposite breast

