#### **At completion of brachytherapy**

- Patient QOL form (Appendix III)
- Treatment Toxicity Form
- Radiotherapy Treatment/Dosimetry Form (Appendix III)

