#### **At 4-6 wks, 6 mo., and 12 months after implant; q 6 months up to 5 years, then annually. Also at progression/relapse and at death**

- Follow-up Form (Appendix III) -- Can be done via clinic visit notes from other physicians involved in patient's care or via telephone follow-up

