#### **At 6 mo. and 12 months after the completion of therapy, then yearly up to 5 years**

- Cosmesis Forms
  - *Patient* (Appendix)

- *Radiation Oncologist* (Appendix III)
- Patient QOL form (Appendix III)

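### Satisfaction is to be measured at completion and at 4-6 weeks, but the only form shown with a satisfaction question is scheduled at neither visit

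*Combined protocol and SAP*

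**What the plan says.** **The aim.** Objective 2.2 reads: "To assess patient satisfaction with breast brachytherapy by a questionnaire pre-brachytherapy, at completion, and post-brachytherapy". Section 10.1.4, headed as the quality-of-life assessment, is more specific: "Patient satisfaction with breast brachytherapy will be assessed by a questionnaire at defined intervals: pre-brachytherapy, at completion, 4-6 weeks post-brachytherapy", followed by 6 months and yearly assessments. It points to attached forms without naming one.

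**The forms.** Item 3 of the Patient Cosmesis Form (Appendix III) asks how satisfied the patient is with the treatment and its results, with four possible answers. The only quality-of-life form in Appendix III is the Spitzer index. Its five items cover activity, daily living, health, support and outlook.

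**The schedule.** Table 8.1 marks the patient cosmesis form before treatment, at 6 months and at 1 year, then yearly to year 5. The cells for during/after brachytherapy and for 4-6 weeks are empty. Section 9.1 lists the cosmesis forms before brachytherapy and then "At 6 mo. and 12 months after the completion of therapy, then yearly up to 5 years". Section 10.1.3 gives matching times: "Cosmetic results will be assessed by both the physician and the patient pre-brachytherapy, at six and twelve months, then annually". Section 8.4 agrees. At completion, 9.1 lists the quality-of-life, toxicity and dosimetry forms. At 4-6 weeks it lists only the Follow-up Form.

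**The concern.** The visits at which satisfaction is to be assessed do not match the visits at which the satisfaction question is asked. A coordinator who follows 8.1 and 9.1 exactly hands out the Spitzer index at completion and has no satisfaction question to ask there or at 4-6 weeks. A patient's view at completion cannot be recovered later, and these early visits are when the experience of the one-week treatment is freshest.

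Two smaller problems go with this. Item 3 is scheduled at baseline, where it cannot measure satisfaction with brachytherapy. And 8.1 marks the quality-of-life questionnaire at 4-6 weeks, while 9.1 does not list it there.

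What is at stake is one secondary objective. Section 10.2 plans only summary statistics for the quality-of-life measures, so no hypothesis test or decision rule depends on these data.

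**Working it through.** The plan states no figure to reproduce. The check sets the passages side by side and counts.

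| Visit | Satisfaction due (10.1.4) | Named in objective 2.2 | Patient Cosmesis Form, item 3 (8.1 and 9.1) | Spitzer index (8.1 / 9.1) |
|---|---|---|---|---|
| Pre-brachytherapy | yes | yes | yes | yes / yes |
| Completion | yes | yes | **no** | yes / yes |
| 4-6 weeks | yes | not separately | **no** | yes / **no** |
| 6 months | yes | as post-brachytherapy | yes | yes / yes |
| Years 1-5 | yes | as post-brachytherapy | yes | yes / yes |

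**Time points.** Section 10.1.4 gives no end to the yearly assessments. Note b to table 8.1 and the matching list in 9.1 stop the patient forms at year 5, so that limit is used.

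- Due under 10.1.4: 1 (pre) + 1 (completion) + 1 (4-6 weeks) + 1 (6 months) + 5 (years 1-5) = 9.
- Item 3 scheduled: 1 (pre) + 1 (6 months) + 5 (years 1-5) = 7.
- Not scheduled: 9 − 7 = 2, namely completion and 4-6 weeks.

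**Baseline.** Three of the four answers to item 3 (options 2 to 4) presuppose that brachytherapy has been given: willingness to choose it again, preference for external beam in hindsight, or dissatisfaction with the implants. The remaining answer, total satisfaction, could at that stage describe only the surgery. The form's code of -1 (not applicable or unknown) is the best available reply. Usable time points: 7 − 1 = 6.

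**Responses not collected**, with the 300 patients of 10.1.1 and 10.2:

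- Against 10.1.4: 2 × 300 = 600.
- Against objective 2.2 alone, where completion is the only specific post-treatment visit without the item: 1 × 300 = 300.

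Both are upper limits, since they assume that every patient reaches the visit and would have answered.

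**The case against.** The strongest reply is that the questionnaire in 10.1.4 is simply the quality-of-life form. The section carries that heading, and its visits match the quality-of-life row of table 8.1 in every column and do not match the cosmesis row. No section names item 3 as the satisfaction measure. On this reading the scheduled questionnaire is collected at every visit in 8.1, the fault is loose wording, and the 600 responses were never planned.

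This may well be how the text arose, and part of it stands: the count depends on item 3 being the satisfaction measure. It does not remove the problem. The Spitzer index does not ask about satisfaction, so the objective still goes unmet at completion and at 4-6 weeks. If the attached forms are instead taken to mean both patient forms at every interval, 10.1.4 contradicts 8.1, 9.1 and 10.1.3.

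Two passages point the other way for 4-6 weeks. Objective 2.2 speaks of evaluating cosmesis at every follow-up, and the Follow-up Form has a box recording whether the patient's cosmesis form was completed. That box is on a form used at all follow-up visits and schedules nothing. The explicit timings in 8.1, 8.4, 9.1 and 10.1.3 outweigh the general phrase, and neither passage reaches the completion visit.

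The Treatment Toxicity Form and the staff-completed first page of the Patient Cosmesis Form are not reproduced. Neither is described as asking about satisfaction, but the finding is limited to the forms shown.

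Finally, the text could be reconciled by narrowing 2.2 and 10.1.4 to the visits already covered, with no new data collection. That is a legitimate choice, but it gives up the completion assessment that objective 2.2 names. Leaving the text as it stands resolves nothing.

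**Conclusion.** The concern holds. Followed as written, the schedule produces no satisfaction data at 2 of the 9 time points that 10.1.4 implies through year 5, and an uninformative value at a third. The other 6 (6 months and years 1-5) are sound. The shortfall is up to 600 responses against 10.1.4, or up to 300 against objective 2.2.

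This rests on three assumptions: item 3 is the intended satisfaction measure, as the only such question in the forms shown; yearly assessment ends at year 5; and all 300 patients would have responded. If the Spitzer index was what the authors meant, the counts fall away, but the objective then names a construct that its instrument does not measure.

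The consequence is confined to a descriptive secondary endpoint. It is worth correcting because the fix is cheap and the early answers cannot be obtained afterwards.

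**What to change.** - In 8.1 and 9.1, add item 3 of the Patient Cosmesis Form at completion and at 4-6 weeks. The cosmesis grade (item 2) keeps its present schedule.
- In 9.1, list the quality-of-life form at 4-6 weeks, to agree with 8.1.
- Omit item 3 at baseline and remove the pre-treatment visit from the satisfaction time points in 2.2 and 10.1.4.
- In 2.2 and 10.1.4, name item 3 as the satisfaction measure and the Spitzer index as a separate quality-of-life measure that keeps its baseline assessment.
- Summarise item 3 by visit and do not pool across visits. The question covers both treatment and results, and early answers will mostly reflect the treatment because cosmetic results have yet to develop.

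The cost is one question at two existing visits, a form revision, and wording changes in four sections (2.2, 8.1, 9.1, 10.1.4). Section 9.1 lets the Follow-up Form be completed from outside clinic notes or by telephone, so patients not seen at 4-6 weeks would need to be asked item 3 by phone or mail. If early satisfaction is not wanted, the minimum is to restrict 2.2 and 10.1.4 to the visits from 6 months onward and still name the two instruments separately.
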